- The edoxaban dosage regimen will be reduced permanently for subjects with moderate renal impairment (eGFR) $\geq 30\%$ to $\leq 50\%$ of normal for the subject's age and size at randomization as determined by the age-appropriate formula: Cockcroft-Gault equation for pediatric subjects ≥ 12 years of age and modified Schwartz equation for pediatric subjects <12 years of age (Appendix 17.7). If a subject experiences a change in renal function from normal to eGFR $\geq 30\%$ to $\leq 50\%$ after randomization, the measurement will be repeated within 1 week to 10 days after correction of the underlying factor's causing pre-azotemia. If the repeat measurement confirms the reduced eGFR, the edoxaban dose will be reduced permanently.

- Additionally, if a subject requires concomitant administration of a certain P-glycoprotein (P-gp) inhibitor (Appendix 17.4.6), the edoxaban dose will be reduced during P-gp administration and re-established to the original dose once P-gp inhibitor administration had concluded.
- Subject is ≤ 28 days old (corrected for gestation age of 38 weeks). This may change based on the IDMC recommendation.

Randomization to Standard of Care Treatment Arm

Standard of care treatment will be dispensed to the subject on a monthly visit schedule. After Month 3, on a case-by-case basis, confirmed by the Sponsor, a 3-month dispense may occur to facilitate subject travel arrangements.

Local SOC sourcing:

The SOC will be provided by the Investigator. Subject will be treated with LMWH, VKA, or SP Xa inhibitors according to the site SOC treatment regimen (see Section 5.1.1.2).

Central/Sponsor Sourcing:

However, if there are regulatory or site hurdles providing the SOC, the Sponsor will provide SOC as enoxaparin or fondaparinux or warfarin as follows:

- Enoxaparin – Subjects will be treated with enoxaparin alone or can be switched to warfarin anytime during the study treatment period.
 - Enoxaparin (LMWH) will be provided to the subjects as solution for subcutaneous (SC) injection in pre-filled syringes with 60 mg/0.6 mL, 80 mg/0.8 mL, and 100 mg/1.0 mL concentration for injection, or as multiple dose vials (for subjects < 10 kg) for injection where allowed per standard clinical practice.
- Fondaparinux – Subjects will be treated with fondaparinux alone or can be switched to warfarin anytime during the study treatment period.

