Edoxaban dosage regimen will be reduced permanently for subjects with moderate renal impairment for the subject's age and size at randomization as determined by the age appropriate formula: Cockcroft-Gault equation for pediatric subjects ≥12 years of age and modified Schwartz equation for pediatric subjects <12 years of age). Refer to Appendix 17.7 for eGFR values below which dose reduction should be implemented.

If a subject experiences a change in renal function from normal to eGFR ≥30% to ≤50% after randomization, the measurement will be repeated within 1 week to 10 days after correction of the underlying factor's causing pre-azotemia. If the repeat measurement confirms the reduced eGFR, the edoxaban dose reduction will be permanent even if the subject experiences an improvement in the eGFR during the course of the study.

^b Dose reduction due to body weight applies only for fixed doses in subjects 12 to <18 years of age:

If body weight increases or decreases from the categories of weight defined at consent, the subject will be dose adjusted. Subjects who are ≥60 kg of body weight at consent and drop below that body weight will receive 45 mg dose at any subsequent visit. Subjects who are ≥30 and <60 kg at consent and increase their weight to ≥60 kg will increase their dose to 60 mg.

^c Edoxaban dosage regimen will be reduced permanently for subject with body weight <5th percentile for age.
Refer to Appendix 17.9.

^d Edoxaban granulation will be diluted with 8 mL water to provide a concentration of 6 mg/mL dosing suspension. If body weight increases or decreases from the categories of weight defined at consent, the subject will be dose adjusted. Subjects who are \geq 60 kg of body weight at consent and drop below that body weight will receive 45 mg dose at any subsequent visit. Subjects \geq 30 and <60 kg at consent increasing their weight to \geq 60 kg will increase their dose to 60 mg.

Note: Dose is based upon weight at corresponding visit.

^e Edoxaban granules are for subjects <12 years of age only. Subjects 12 to <18 years of age should use crushed edoxaban tablets. For those subjects cannot swallow whole tablets, edoxaban tablets may be crushed and mixed with 2 to 3 ounces of water and immediately administered by mouth or through a gastric tube. The crushed tablets may also be mixed into applesauce and immediately administered..

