5.3.1. Edoxaban Dose Reduction

During the treatment period, a subject may reduce the dose of edoxaban for any of the following reasons ([Table 5.1](#)):

- eGFR is 30-50% of normal for age and size ([Appendix 17.7](#)).
- Subject is receiving concomitant treatment with P-gp inhibitors.
- Body weight <5th percentile of subject's age (see [Appendix 17.9](#)).
- Subject is \leq 28 days old (corrected for gestation age of 38 weeks). This may change based on the IDMC recommendation.

For subjects receiving P-gp inhibitors, the dose of edoxaban will only be reduced during the administration of the concomitant P-gp inhibitor. Subjects experiencing eGFR or body weight reduction will maintain their reduced edoxaban dose for the duration of the study. Once the subject turns $>$ 28 days old, the dose may be increased to 0.8 mg/kg.

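### Table 5.1 footnote b sets the dose after crossing 60 kg in full-dose milligrams with no exception for a permanent renal reduction, so one adolescent can be due 60, 45 or 30 mg

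*Combined protocol and SAP*

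**What the plan says.** Table 5.1 (Section 5.1.1.1.1) gives two tablet doses for each of the two main weight bands at 12 to <18 years. At 60 kg or more the dose is 60 mg, reduced to 45 mg. At 30 to <60 kg it is 45 mg, reduced to 30 mg.

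Footnote b covers a change of weight band during treatment. On gain: "Subjects who are ≥30 and <60 kg at consent and increase their weight to ≥60 kg will increase their dose to 60 mg". On loss, subjects of 60 kg or more at consent who "drop below that body weight will receive 45 mg dose at any subsequent visit".

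Footnote a covers renal impairment: "Edoxaban dosage regimen will be reduced permanently for subjects with moderate renal impairment". For impairment that appears after randomization and is confirmed on repeat, "the edoxaban dose reduction will be permanent even if the subject experiences an improvement in the eGFR during the course of the study". The Protocol Synopsis repeats the permanence.

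Section 5.3.1 adds: "Subjects experiencing eGFR or body weight reduction will maintain their reduced edoxaban dose for the duration of the study".

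A note under footnote d, which belongs to the granule dosing, says: "Dose is based upon weight at corresponding visit".

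**The concern.** The 60 mg and 45 mg in footnote b are the full doses of the two weight bands. Nothing in the footnote limits them to subjects on the full dose, and the upward step is worded as an instruction. It is also the only text that deals specifically with a tablet subject crossing 60 kg, so it is what a pharmacist would look up when that happens.

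The stake is patient safety: a site that applies the sentence as written gives the full anticoagulant dose to an adolescent whose renal reduction the same table calls permanent. Body weight is scheduled at Months 1, 2, 3, 6, 9 and 12 (Table 17.1), and treatment can run to 12 months, so a crossing can occur and be seen. Section 1.1 names renal insufficiency and nephrotic syndrome among the conditions behind paediatric thrombosis, so renally reduced adolescents are plausible. Section 5.1.2 describes the reduction factors given to the interactive response system at randomization; it does not say how the system handles a later weight change in a reduced subject.

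**Working it through.** The plan gives no figure to reproduce, so the check is to read off the dose each source gives to the same subject.

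**Inputs (Table 5.1, 12 to <18 years).** Full dose: 60 mg at ≥60 kg, 45 mg at 30 to <60 kg. Reduced dose: 45 mg and 30 mg. Reduced over full: 45/60 = 0.75 and 30/45 = 0.67.

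| Source | Renally reduced, on 30 mg, rises to ≥60 kg | Renally reduced, on 45 mg, falls below 60 kg |
|---|---|---|
| Footnote b, read literally | 60 mg | 45 mg |
| Dose Reduction column, current weight row | 45 mg | 30 mg |
| Section 5.3.1, read as a milligram amount | 30 mg | 45 mg |

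**Weight gain.** Going from 30 to 60 mg is 60/30 = 2.0. This splits into two steps:
- 45/30 = 1.5, the table's own step at 60 kg within the reduced column;
- 60/45 = 1.33, the loss of the renal reduction.

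The product is 1.5 × 1.33 = 2.0. Against the column, only the 1.33 is excess.

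Per kilogram, taking 59 kg before and 60 kg after as an illustration, the starting dose is 30/59 = 0.508 mg/kg. Afterwards:
- 60 mg: 60/60 = 1.00 mg/kg, ratio 1.97;
- 45 mg: 45/60 = 0.75 mg/kg, ratio 1.48;
- 30 mg: 30/60 = 0.50 mg/kg, ratio 0.98.

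**Weight loss.** Staying on 45 mg takes the subject from 45/60 = 0.750 to 45/59 = 0.763 mg/kg, a ratio of 1.017 (+1.7%). The column would give 30/59 = 0.508 mg/kg. The 45/30 = 1.5 between the two answers is again the table's step at 60 kg.

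**Do the other texts settle the order?** Footnote a makes the reduction permanent but names no dose after a weight change. Section 5.3.1 keeps the reduced dose but does not say whether that means the status or the milligrams. The note under footnote d points to the current weight row, but it sits with the granules and does not say which column applies. None of them refers to footnote b.

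**The case against.** The best reply is that the protocol, read as a whole, does not send anyone back to 60 mg. Footnote b opens by describing itself as a rule on body weight for fixed doses. Renal reduction is governed by footnote a, and Section 5.3.1, headed as the section on dose reduction, speaks directly about these subjects. The natural reading, current weight row and reduced column, is safe. All of that stands as evidence of intent. It does not remove the conflict: the specific rule for crossing 60 kg still prescribes 60 mg without qualification, and the texts that rule this out disagree between 45 and 30 mg.

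A reader might infer more than the documents support:

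- **That no correct dose is stated.** Table 5.1 does print a reduced dose for each of the two weight bands. What is missing is an order of precedence.
- **That weight loss causes an overdose.** It brings no rise in milligrams, and footnote b and Section 5.3.1 agree on 45 mg there. Only the column differs.
- **That subjects below the 5th percentile for weight would be moved to 60 mg.** They have their own row in Table 5.1. Footnote c says "Edoxaban dosage regimen will be reduced permanently for subject with body weight <5th percentile for age", Section 5.3.1 names body weight alongside eGFR, and the column entry is not applicable, so no other reduced dose competes. The text settles these subjects at 30 mg.
- **That P-gp inhibitor subjects are left in doubt.** Section 5.5 and Appendix 17.4.6 require a reduction during inhibitor use, with amiodarone the only exemption. Footnote b only needs wording consistent with them.

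It is also fair to say that the documents give no exposure data favouring 45 over 30 mg after a weight gain in a renally reduced subject. That choice belongs to the sponsor.

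**Conclusion.** The point holds as a dosing-safety clarification that should be made. For a renally reduced subject on 30 mg who reaches 60 kg, three places in the protocol give 60, 45 and 30 mg. The 60 mg is clearly unintended, yet it is what footnote b orders, at 1.33 times the column dose. In the opposite direction the sources give 45 or 30 mg, an inconsistency without a dose rise.

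This rests on a literal reading of footnote b and on reading Section 5.3.1 as a milligram amount; if 5.3.1 means reduced status, it agrees with the column at 45 mg. The point reaches only edoxaban subjects aged 12 to <18 years on a permanent renal reduction who cross 60 kg during 3 to 12 months of treatment. Their number is not given and is likely to be small. The documents give no exposure or bleeding figure for the excess dose, so no clinical effect can be sized. Sample size and the primary analysis are unchanged.

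**What to change.** In footnote b, limit the 45 mg and 60 mg doses to subjects not on a dose reduction. Refer renally reduced subjects, and P-gp inhibitor subjects while on the inhibitor, to the Dose Reduction column for their current weight row: 45 mg at ≥60 kg, 30 mg at 30 to <60 kg.

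Align Section 5.3.1 by saying that, for renal subjects, the reduced status is kept and the milligrams follow current weight. If the sponsor prefers to keep 30 mg after a weight gain, state that there instead and make footnote b agree. Either way, weight gain alone must not restore 60 mg.

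The cost is one or two sentences in footnote b and one in Section 5.3.1, with no extra patients, visits or procedures.

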5.1.1.2. Edoxaban dose recommended for <12 years old pediatric subjects

Subjects of age <2 years will have dose recommendations based on the PK and safety data from same age cohort in U157 study and subjects evaluated for edoxaban exposure in the previous older cohort in U312 study. The PK and safety data will be reviewed by the IDMC (Section 15.9) who will approve the start of the next younger age cohort. Based on the IDMC review of Cohort 1 data from DU176b-D-U312 and corresponding cohort data from study DU176b-A-U157, the proposed dose that was safe and effective for VTE treatment was 1.2 mg/kg body weight for Cohort 2 (6 to <12 years) (Table 5.1), 1.4 mg/kg body weight for Cohort 3 (2 to <6 years), 1.5 mg/kg, for Cohort 4 (6 months to <2 years), 0.8mg/kg for Cohort 5 (>28 days to <6 months), and will be determined by the IDMC for Cohort 5 (38 weeks gestation to \leq 28 days).

Doses for all subsequent age cohorts will be made by separate notifications to the investigative sites, outside the content of this protocol, and after the IDMC has approved the proposed edoxaban doses. An official notification will be sent when select age cohorts can begin randomization to either SOC or edoxaban treatment. In addition, a notification will indicate that Day 5 PK/PD edoxaban exposure evaluation will no longer be necessary for future subjects randomized to edoxaban in the corresponding age cohort.

Subjects of age <12 years will receive edoxaban granules for oral suspension (60 mg) and will be dosed on an mg/kg basis. Check the body weight prior to dosing and adjust dosage accordingly. Frequency of dosage changing is up to the Investigator's discretion, but the maximum dose would not exceed 45 mg once a day (QD).

5.1.1.2. Standard of Care Treatment Arm

SOC treatment will be dispensed to the subject on a monthly visit schedule. After Month 3, the distribution of SOC may be for a 3-month period to align with the visit schedule, with the Sponsor's approval. Subjects will receive SOC anticoagulant according to the site's SOC treatment, as follows (alone or combination):

- LMWH (alone or followed with VKA)
- SP Xa inhibitors (alone or followed with VKA)
- Vitamin K antagonist (VKA)

In case of centrally sourced SOC treatment, the Sponsor will only provide enoxaparin as LMWH, fondaparinux as SP Xa inhibitor, or warfarin as VKA with limited presentations. The subject will be treated with enoxaparin or fondaparinux or warfarin/heparin, with the following suggestion:

- Enoxaparin – Subjects will be treated with enoxaparin alone or can be switched to warfarin anytime during the study treatment period. Single dose (pre-filled syringe) or as multiple dose vials (for subjects <10 kg) for injection where allowed per standard clinical practice will be provided to the subject. Initial treatment age-dependent dose of enoxaparin:
 - Age <2 months: 1.5 mg/kg dose twice a day
 - Age ≥ 2 months: 1.0 mg/kg dose twice a day
- Fondaparinux – Subjects will be treated with fondaparinux alone or can be switched to warfarin anytime during the study treatment period.
 - Dosing of 0.1 mg/kg/day (0.05 mg/kg/day for subjects with renal disease).
 - If the appropriate required dose cannot be administered with the pre-filled syringes, the site should consider using alternative SOC treatment options.
- Warfarin will be started on Day 1. Heparin will be discontinued when INR ≥ 2.0 and ≤ 3.0 for 2 consecutive measurements obtained at least 24 to 48 hours apart. The subject will continue warfarin treatment for the remainder of the study treatment period.
 - Additional information on dosing and dose adjustment (Appendix 17.2)

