 - Fondaparinux will be supplied as solution for SC injection in pre-filled syringes (2.5 mg/0.5 mL, 5.0 mg/0.4 mL, 7.5 mg/0.6 mL, 10.0 mg/0.8 mL, and where available 1.5 mg/0.3 mL).

- Warfarin will be supplied as tablets (0.5 mg, 1.0 mg, and 3.0 mg).

For subjects in whom clinicians prescribe warfarin, then warfarin will be started on Day 1. Heparin (enoxaparin or fondaparinux or UFH depending on the therapy received during pre-randomization period) will be discontinued when INR ≥ 2.0 and ≤ 3.0 for 2 consecutive measurements obtained at least 24 to 48 hours apart. The subject will continue warfarin for the remainder of the study treatment period.

Study Endpoints:

All safety and efficacy endpoints described below will be adjudicated in a blinded manner by the Clinical Events Committee (CEC).

Primary Efficacy Endpoint:

The primary efficacy endpoint is a composite endpoint consisting of the incidence of symptomatic recurrent venous thromboembolic disease, death as a result of VTE, and no change or extension of thrombotic burden (Section 7.1) during the first 3 months period.

-For subjects in Cohort 5, (ie, <6 months old), the primary efficacy endpoint is a composite endpoint consisting of the incidence of symptomatic recurrent VTE, death as a result of VTE, and no change or extension of thrombotic burden within 6 to 12 weeks + 3 days.

Secondary Efficacy Endpoints:

The secondary efficacy endpoints include:

- A composite endpoint consisting of symptomatic recurrent venous thromboembolic disease, death as a result of VTE, and no change or extension of thrombotic burden from randomization to the date of the last dose of study drug + 30 days .
- The individual components of the primary efficacy endpoint during the first 3-month period (for Cohort 5, the intended duration of treatment is 6-12 weeks):
 - Symptomatic recurrent VTE
 - Death as a result of VTE
 - No change or extension of thrombotic burden
- All-cause mortality from randomization to last dose + 30 days.

- The DVT, Catheter-related thrombosis, PE, sinovenous thrombosis events within and after the first 3-month treatment period (for Cohort 5, the intended duration of treatment is 6-12 weeks).

Net Clinical Outcome Endpoint:

- Composite of symptomatic recurrent VTE events, death as a result of VTE, and major and CRNM bleeding that occurred from the date of the first dose of study drug to the date of last dose of study drug + 30 days.

Safety Endpoints:

The safety endpoints are:

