1. INTRODUCTION

1.1. Background

The clinical presentation of pediatric venous thromboembolic (VTE) disease includes many manifestations, such as catheter-related thrombosis, pulmonary embolism (PE), deep vein thrombosis (DVT), and sinovenous thrombosis. The majority of pediatric subjects (>95%) with VTE have at least 1 clinical risk factor.

Currently, the presence of a central venous catheter is the most important acquired trigger for the development of venous thromboembolic disease in pediatric subjects, contributing to >90% of all neonatal thrombi and more than half of all thrombi in the older children^{1, 2 3, 4}. Several mechanisms play a role in the development of catheter related thrombosis, including vessel wall injury by the catheter or infused substances (especially parenteral nutrition), compromised blood flow, and thrombogenic effects of the catheter material⁵. Catheter-related thrombi develop in children with long-term venous access devices for diseases such as malignancy, intestinal failure, renal insufficiency, and cystic fibrosis and in children with short-term catheters on the intensive care unit or for cardiac catheterization^{6, 7, 8}. Other important risk factors for pediatric thrombosis are congenital heart disease, surgery, immobilization, malignancy, nephrotic syndrome, sepsis, and estrogen treatment. The presence of congenital prothrombotic disorders contribute to the development of pediatric venous thrombosis, as well⁹.

Increasing numbers of pediatric subjects with chronic diseases will require anticoagulation as the incidence of VTE events rises due to hypercoagulability and the use of central venous catheters¹⁰.

Currently, the majority of pediatric thrombi are treated with low molecular weight heparin (LMWH) or unfractionated heparin (UFH) followed by LMWH or vitamin K antagonists (VKAs) for a total of 3 to 6 months¹¹. More recently, data exists for the use of fondaparinux in children^{12, 13}. Subjects should receive LMWH, UFH, or fondaparinux for at least 5 days following diagnosis of VTE. Guidelines recommend starting VKA on the first treatment day because of slow onset of action. LMWH, UFH, or fondaparinux may be discontinued when the VKA has reached its therapeutic level, as indicated by an international normalized ratio (INR) ≥ 2.0 for 2 or more measurements at least 24 hours apart. Many pediatric subjects have severe underlying diseases which preclude early oral treatment and thus LMWH is continued.

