5.2.4.2. Instruct the subject randomized to SOC treatment

Subjects randomized to SOC treatment arm will receive SOC anticoagulant according to the study site's SOC treatment as follows (alone or combination):

- LMWH (alone or followed with VKA)
- SP Xa inhibitors (alone or followed with VKA)
- Vitamin K antagonist (VKA)

If Investigators choose to use centrally sourced SOC treatment from Sponsor, the subject will be treated as follows:

- For subjects randomized to enoxaparin: for neonates or children receiving either once- or twice-daily therapeutic enoxaparin the drug should be monitored to a target anti-FXa level of 0.5 to 1.0 units/mL in a sample taken at 4 hours post-dose for therapeutic levels. Monthly monitoring of anti-FXa levels is recommended. More frequent anti-FXa levels can be recommended as per Investigator's decision.
- For subjects randomized to fondaparinux: dosing of 0.1 mg/kg/day (0.05 mg/kg/day for subjects with renal disease). Monitoring fondaparinux levels (0.5- 1 mg/L) can be recommended as per Investigator's decision.
- For subjects randomized to warfarin: the dose should be titrated to achieve a target INR of 2.5 (≥ 2.0 and ≤ 3.0). Visits will be at the discretion of the Investigator and captured as unscheduled visits for data collection. Adjustment of the maintenance dose of VKA will be dependent on INR monitoring as follows:
 - INR = 2.0 to 3.0, no change in dose
 - INR = 1.1 to 1.4, increase dose by 20%

- INR = 1.5 to 1.9, increase dose by 10%
- INR = 3.1 to 3.5, decrease dose by 10%
- INR >3.5, hold VKA until INR is <3.5, then decrease dose by 20% when restarted.

To initiate SOC post screening, it is recommended to test infants and children every 4 weeks once a stable dose of VKA has been achieved. However, depending on the site's clinical practice and PI's discretion, the subjects can be tested at the physician's discretion and/or according to local practice. More frequent INR testing is recommended in infants and children receiving VKA with any change in diet or medication or when an illness occurs. An unscheduled visit will need to be performed to document the discretionary INR measurement and potential VKA dosage change as an unscheduled visit day.

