If a therapeutic INR (≥ 2.0 on 2 separate measurements at least 24-48 hours apart or a single supratherapeutic INR >3.0) is not achieved within 12 days (by Day 12) after starting LMWH and warfarin, the Investigator may be contacted by a study physician for discussion and guidance.

Guidance on dosing and dispensing is provided in Appendix [17.2](#).

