- Safety data analysis on Day 5 subjects in the prior older age cohort in U312
- PK analysis of the subjects in the next younger age cohort in U157.

- Safety data analysis on the subjects of the next younger age cohort in U157.

PK and safety data will be reviewed by an IDMC, (Section 15.9) who will approve the start of the next younger age cohort.

In each age cohort, if the estimated median AUC based on the observed PK data in participating subjects in the Day 5 PK assessment is less than 1.5-fold the median AUC from the simulated subject population profiles (over-exposure and under-exposure), the enrollment of subjects in the corresponding age cohort will continue and enrollment in the next younger age cohort can begin.

The following will be performed at this visit:

- Review dosing instructions
- Safety review for AEs/SAEs
- Review for endpoint events (VTE, bleeding)

The Investigator will use discretion to decide when and how often to repeat INR or anti-FXa levels or aPTT measurements or fondaparinux levels. These measurements will be taken in the clinic, or alternatively, optional site-specific local laboratory (Appendix 17.2).

6.3.2. Subjects randomized to the SOC treatment arm:

Standard of Care treatment will be dispensed to the subject on a monthly visit schedule. After Month 3, dispense may be provided for a 3-month period to align with the visit schedule based on approval of the Sponsor. SOC will be provided by the Investigator. Subject will be treated with LMWH, VKA, or SP Xa inhibitors according to the site SOC treatment (Section 5.1.1.2). However, if there are regulatory or site hurdles providing the SOC, the Sponsor will provide SOC as enoxaparin or fondaparinux or warfarin (see below).

If Investigators choose to use the SOC supplied by the Sponsor, the subject will be treated as follows:

- Enoxaparin – Subjects will be treated with enoxaparin alone or can be switched to warfarin anytime during the study treatment period.
- Fondaparinux – Subjects will be treated with fondaparinux alone or can be switched to warfarin anytime during the study treatment period.

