- For subjects in whom clinicians prescribe warfarin, this will be started on Day 1. Heparin (exoxaparin or fondaparinux or UFH depending on the therapy received during pre-randomization period) will be discontinued when INR ≥ 2.0 and ≤ 3.0 for 2 consecutive measurements obtained at least 24 to 48 hours apart. The subject will continue warfarin for the remainder of the study treatment period.

The Investigator will use discretion to decide when and how often to repeat INR or anti-FXa levels or aPTT measurements or fondaparinux levels. These measurements will be taken in the clinic, or alternatively, optional site-specific local laboratory (Appendix 17.2).

6.3.3. Monthly Visits (Months 1 and 2; Visits 3 and 4) for both arms:

Starting with the Month 1 visit, subjects will return to the clinic every 30 days \pm 5 days (depending on the visit, see Schedule of Events in Appendix 17.1) until the Month 3 visit (Visit 5) or study withdrawal. For Cohort 5, the subjects may return to the clinic earlier after the first month, depending on the duration of the therapy (at least 6 to 12 weeks) and imaging at 6 weeks for thrombus resolution.

During study drug interruptions and after study drug discontinuation, subjects will be followed for efficacy and safety endpoints and SAEs until the Month 3 visit (Visit 5) or earlier in Cohort 5 subjects (6-12 weeks). A 30 day Follow-Up Visit (Visit 9) for safety assessment is required after the Month 3 visit (for Cohort 5, the intended duration of treatment is 6 to 12 weeks).

At these monthly on-site visits, anti-FXa levels assessments and aPTT measurements will be performed for the subjects on SOC with LMWH or SP Xa inhibitor, fondaparinux levels if applicable, and INR assessments will be performed for the subject on SOC with VKA. Additional interim visits may be scheduled, at the Investigator's discretion, for anti-FXa levels/INR monitoring.

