17.2. Additional Information on Investigational Product Use in Pediatric Subjects

Recommendations per CHEST 2012 Guidelines²⁶

Table 17.2: Doses of LMWH (enoxaparin) used in Pediatric Subjects

Drug	Age	Initial Treatment Dose	Initial Prophylactic Dose
Age -dependent Dose of Enoxaparin	<2 months	1.5 mg/kg/dose q12h	0.75 mg/kg/dose q12h
	>2 months	1.0 mg/kg/dose q12h	0.5 mg/kg/dose q12h
Enoxaparin has 110 anti-factor Xa units/mg			

Table 17.3: Protocol for Anticoagulation Therapy to maintain an INR between 2.0 and 3.0 for Pediatric Subjects (Warfarin treatment)

1	Day 1: if the baseline INR is 1.0 to 1.3: Dose 0.2 mg/kg orally	
2	Loading 0.2 mg/kg Days 2-4: if the INR is:	
	INR	Action
	1.1 - 1.3	Repeat initial loading dose
	1.4 - 1.9	50% of initial loading dose
	2.0 - 3.0	50% of initial loading dose
	3.1 - 3.5	25% of initial loading dose
	>3.5	Hold until INR \leq 3.5; then restart at 50% decreased dose
3	Maintenance oral anticoagulation dose guidelines:	
	INR	Action
	1.1 - 1.4	Increase by 20% of dose
	1.5 - 1.9	Increase by 10% of dose
	2.0 - 3.0	No change
	3.1 - 3.5	Decrease by 10% of dose
	>3.5	Hold until INR \leq 3.5; then restart at 20% decreased dose

INR = international normalized ratio

Table 17.4: Doses of Fondaparinux

Fondaparinux Doses	Target Therapeutic Fondaparinux Level
0.1 mg/kg, once a day	0.5-1 mg/L (blood drawn at 3 hours post-dose)
0.05 mg/kg/day (for subjects with renal disease).	
Dose Adjustment of Fondaparinux	
Fondaparinux Level (mg/L)	Doses Adjustment
<0.3	Increase dose by 0.03 mg/kg
0.3 - 0.5	Increase dose by 0.01 mg/kg
0.5 - 1	No change
1 - 1.2	Decrease dose by 0.01 mg/kg
>1.2	Decrease dose by 0.03 mg/kg

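### For sponsor-supplied warfarin, the heparin-stop rule carries an INR ceiling of 3.0, so an overshoot postpones the written trigger for stopping heparin

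*Combined protocol and SAP*

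**What the plan says.** The rule appears three times, each time in text about SOC supplied centrally by the sponsor.

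- Section 5.1.1.2: "Heparin will be discontinued when INR ≥ 2.0 and ≤ 3.0 for 2 consecutive measurements obtained at least 24 to 48 hours apart". The list holding this bullet is introduced as a suggestion.
- Synopsis, under central sourcing: heparin "will be discontinued when INR ≥ 2.0 and ≤ 3.0 for 2 consecutive measurements obtained at least 24 to 48 hours apart".
- Section 6.3.2: heparin "will be discontinued when INR ≥ 2.0 and ≤ 3.0 for 2 consecutive measurements", under the lead-in "If Investigators choose to use the SOC supplied by the Sponsor, the subject will be treated as follows".

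Locally sourced SOC follows the site's own regimen (Section 5.2.1) and lies outside the rule.

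Four other places bear on the same step.

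- Section 1.1 says that the parenteral drug may be stopped once the vitamin K antagonist (VKA) has become therapeutic, "as indicated by an international normalized ratio (INR) ≥ 2.0 for 2 or more measurements at least 24 hours apart". It sets no upper limit.
- Section 5.2.4.2 gives the warfarin target as INR 2.5 (range 2.0 to 3.0). Above the range it acts on warfarin alone: "INR = 3.1 to 3.5, decrease dose by 10" per cent, and hold above 3.5. Table 17.3 does the same during loading: at 3.1 to 3.5 give "25% of initial loading dose", and hold above 3.5.
- Section 5.2.4.2 also allows a study physician to contact the investigator if a therapeutic INR (two values of 2.0 or more, "at least 24-48 hours apart or a single supratherapeutic INR >3.0) is not achieved within 12 days") has not been reached. Here an INR above 3.0 counts as therapeutic.
- Section 17.5, on moving from edoxaban to a VKA, stops heparin at an INR of 2.0 or more, although its preceding paragraph gives the therapeutic level as 2.0 to 3.0.

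**The concern.** Heparin overlaps with warfarin to cover the child until warfarin works. An INR above 3.0 is past the target range, yet under the written rule it does not count towards stopping heparin and it breaks a run of qualifying values. A child at 2.1 then 2.2 meets the rule; a child at 3.2 then 3.4 does not. The stop trigger therefore moves later for the more anticoagulated child.

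Nothing else in the SOC-arm text ties stopping heparin to a high INR. Section 5.2.4.2 and Table 17.3 adjust warfarin only. Appendix 17.6 withholds all anticoagulants, but its trigger is ongoing major bleeding. The Day 12 contact is no safety net either, because a child who has overshot counts as having reached a therapeutic INR.

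At stake is the time some children on sponsor-supplied warfarin may spend on two anticoagulants with an INR above target. No statistical quantity in the plan depends on it.

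**Working it through.** The plan gives no figure to reproduce, so the check applies two rules to the same INR series.

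- Rule A (Synopsis, Sections 5.1.1.2 and 6.3.2): heparin stops at the second of two consecutive values that both lie between 2.0 and 3.0.
- Rule B (ceiling deleted, in line with Section 1.1): heparin stops at the second of two consecutive values that are both 2.0 or more.

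Delay = (stopping position under A − stopping position under B) × spacing between measurements. The INR series are illustrative assumptions. Spacing is assumed to be 24 h or 48 h; the protocol states only a minimum and leaves repeat testing to the investigator (Sections 6.2 and 6.3.2).

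| INR series | A stops at value | B stops at value | Difference |
|---|---|---|---|
| 2.4, 2.6 | 2 | 2 | 0 |
| 3.2, 2.8, 2.6 | 3 | 2 | 1 interval: 1 × 24 = 24 h to 1 × 48 = 48 h |
| 2.4, 3.2, 2.8, 2.6 | 4 | 2 | 2 intervals: 2 × 24 = 48 h to 2 × 48 = 96 h |
| 2.4, 2.8, 1.8 | 2 | 2 | 0 |
| 2.4, 3.2, 1.8 | not met | 2 | Under B heparin is already off when the INR reaches 1.8; under A it is still running |
| 3.6, 3.8 | not met | 2 | Under B heparin stops while warfarin is also on hold |

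On a given pair of values the rules disagree exactly when both are 2.0 or more and at least one exceeds 3.0. Rows 2 and 3 show the cost of the ceiling. Rows 5 and 6 show the cost of removing it: after an overshoot followed by a fall, or while warfarin is held, the child may for a time have less cover. Row 4 shows that a fall below 2.0 can follow either rule.

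The documents give neither the number of children on sponsor-supplied warfarin nor how often the INR exceeds 3.0 during overlap, so no count of affected children or total delay can be derived.

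**The case against.** The strongest defence is that the ceiling is deliberate. Section 1.1 is background and permissive, so waiting for two in-range values does not formally contradict it. The range used is the protocol's own warfarin target. Because warfarin is cut or held above 3.0, two in-range values could be taken to show a stable dose before heparin is withdrawn. Removing the ceiling has a cost of its own, as rows 5 and 6 of the table show.

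Part of this stands. Section 1.1 is not a study instruction, and the downside is real and must be handled in the fix. The stability argument carries less weight. The protocol never offers it, and two consecutive values of 2.0 or more on separate days already give some assurance that the effect persists.

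A reader might infer three stronger things that the documents do not support.

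- That the protocol obliges sites to continue heparin above 3.0. The text does not say that heparin may stop in no other circumstance, and Sections 5.3 and 5.6.3 let the investigator interrupt or stop study drug. Section 15.5 does bar deviations other than to remove an immediate hazard, so relying on discretion is less comfortable than having a correct rule.
- That the Day 12 text contradicts the stop rule. It governs a discretionary contact and is not a heparin-stop rule; both can be followed at once. It shows only that the protocol elsewhere regards an INR above 3.0 as therapeutic. Section 17.5 gives partial support at most, since its two statements differ on the ceiling.
- That the rule inflates SOC-arm bleeding and so tilts the safety comparison towards edoxaban. Nothing in the documents allows that to be estimated.

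**Conclusion.** The point holds as a minor patient-safety matter. In sponsor-supplied warfarin, the written heparin-stop criterion is not met when an INR exceeds 3.0, and this postpones the stated trigger for ending double anticoagulation. It departs from the guideline-based description in Section 1.1 and fits poorly with the Day 12 definition of a therapeutic INR.

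The conclusion rests on a literal reading of wording that appears in three places, only one of which is softened as a suggestion. The 24 to 96 hour delays illustrate the mechanism under assumed INR series and spacings; they do not estimate what happens in the trial. Investigator discretion limits the practical effect. The primary non-inferiority test, power and sample size are unaffected. Confidence is medium.

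**What to change.** Delete the upper limit of 3.0 from the heparin-stop rule in the Synopsis and Sections 5.1.1.2 and 6.3.2, so that heparin stops after two consecutive INRs of 2.0 or more at the stated spacing. Keep 2.0 to 3.0 as the warfarin titration range in Sections 5.2.1 and 5.2.4.2. Stopping on a single INR above 3.0 is not proposed.

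To cover the downside, add one sentence: after heparin stops, and in particular after an overshoot or while warfarin is held above 3.5, the INR is rechecked, and heparin is resumed at the investigator's discretion if it falls below 2.0. Notify the sites that use sponsor-supplied warfarin.

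The cost is one phrase removed in three places, one sentence added and a site notification, plus INR rechecks in the children concerned. The analysis and sample size do not change.
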